## 7.6 DEXA Imaging

Dual Energy X-ray Absorptiometry (DEXA) will be used to document body composition, quantifying fat mass as well as bone mineral density and lean mass. Participants will be required to lie supine for approximately 15 minutes without moving in order to obtain the images. The same DEXA scanner will be used for all visits. The total dose of 8 microSv is equivalent to that received, on average in the UK, from natural sources of background radiation in approximately 32 hours. This dose corresponds to a negligible risk of cancer induction, estimated as around 1 in 3 million

## 7.7 Indirect Calorimetry

Indirect Calorimetry will be undertaken to assess Basal Metabolic Rate (BMR) using a Gas Exchange Measurement instrument. BMR typically falls with weight loss in obese patients so we would like to see if this also happens in patients with FPLD. Participants are advised to avoid any vigorous exercise and caffeine on the day prior to calorimetry. A standardised evening meal based on their weight and predicted or known (DEXA) body composition will be provided to the participant on the day prior to calorimetry followed by overnight fasting. The measurement will be undertaken by the technician at 7.30 am in the participant's own room at the WTCRF.

## 7.8 Oral Glucose Tolerance Test (OGTT)

This procedure allows the measurement of glucose tolerance and Insulin sensitivity. It involves fasting from 10 pm and then having a venous catheter inserted into the upper limb. A base-line set of bloods will be drawn prior to a drink of 75g of anhydrous glucose dissolved in water. Blood sampling will be taken every thirty minutes for the duration of the 3 hour test. In total 120 ml of blood will be drawn (approximately 7 tablespoons).

## 7.9 Fat and muscle (vastus lateralis) biopsies

Fat and skeletal muscle biopsies may be undertaken for histological, genetic or biochemical analysis. The muscle biopsy is done under local anaesthetic on the outer side of the thigh and involves the use of a blunt hollow needle to get a piece of muscle tissue from the leg.

The fat biopsy is performed under local anaesthetic. The incision will be approximately 3cm long, in the left lateral peri-umbilical area 5cm to 10cm from umbilicus, but may vary a little from patient to patient depending on their vasculature, build and access to the fat layer. The tissue in the centre of

the incision will be grasped with forceps, pulled up and gently cut and an appropriately sized chunk of fat will be removed.

### 7.10 Questionnaires

Questionnaires will be undertaken to measure psychosocial factors. The following five separate self-administered questionnaires will be used:

- GAD-7 will be used to measure anxiety
- PHQ-9 will be used to measure depression
- EQ-5D-3L will be used to measure quality of life
- AEBQ (adult eating behaviour questionnaire) will be used to measure eating behaviour and appetite
- TFEQ (three factor eating questionnaire) will be used to measure the cognitive and behavioural domains (or 'factors') of eating: cognitive restraint (CR), disinhibition and hunger

### 7.11 Urine Sample

Participants will be asked to provide a urine sample. A 5-mL portion of the urine sample will be centrifuged for 5 min at 2500 rpm to remove all sediment and particulate matter. A 500 µL fraction of the centrifuged urine will then be pipetted into a 1.5-mL plastic microcentrifuge tube. The urine will be analysed for changes in 8-iso-PGF2a, a validated marker of reactive oxygen species accumulation. It is expected to be fall following weight loss.

## 8. Data Protection

At enrolment into the study, participants will be assigned a unique identifier code. An electronic copy linking identifiable personal details to the unique identifier code will be stored on a secure server on an NHS computer. A hard copy will be retained in the study site file located in a locked cabinet and office at the Institute of Metabolic Science (IMS). Access to the room is restricted to the clinical research team conducting the study and access to the facility is permitted to authorised personnel only allowing only members of the study team to retain access to the participant's true identities.

Biological samples collected and stored during the study will be labelled with the unique identity code, no identifiable personal details will be included. Samples will be stored at the Wellcome Trust-MRC Institute of Metabolic Science until the time of analysis. Data obtained from biochemical analysis/ultrasound investigations undertaken by core departments at Cambridge University Hospital will be accessed via the EPIC computer system. This will include identifiable information however it is only accessible to authorised CUH NHS personnel via password protection of the programme.

Magnetic Resonance scans performed at the Wolfson Brain Imaging Centre (WBIC) will be stored securely within the University of Cambridge. These scans will be stored for 10 years. Participant identifiers will be linked to the scans and accessible to WBIC staff.

REDCap is a mature, secure, web application for building and managing research databases and will be used to collect all demographic and other measures related to the study, no identifiable

information will be collected here. All data held in REDCap is anonymised and can therefore be accessed, in real time, by the research team outside of the Department once they have been issued with the appropriate logins.

Electronic files collating data will be anonymised using the unique identifier code; they will be retained in encrypted files on a password protected computer. Computers will be located at the Wellcome Trust-MRC Institute of Metabolic Science, within a locked office where access is restricted to the research team. Data analysis will be undertaken at the same location. Data collected during the study will be retained for 15 years.

## 9. Statistics

There is no control group in this pilot study; participants will serve as their own controls i.e. before and after analysis.

Statistical analyses will be performed using commercially available software. Parametric data will be presented as mean +/- standard deviation with statistical comparisons performed using the Student's t test. Non-parametric data represented as median (interquartile range) and comparisons will be performed using a Wilcoxon signed rank test. Changes of sequential data within experiments were evaluated by repeated measures ANOVA. Correlations will be assessed using the Spearman rank test. The null hypothesis is rejected at a significance threshold of  $p < 0.05$ .

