### 3.2 Primary Endpoint

A reduction in HbA1c at 12 weeks

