### 3.3 Secondary Endpoints

- A reduction in HbA1c at 1 year
- A reduction in fasting glucose at 12 weeks and 1 year
- A reduction in triglycerides at 12 weeks and 1 year
- A reduction in liver fat at 12 weeks and 1 year
- A reduction in pancreatic fat at 12 weeks and 1 year
- An increase in insulin sensitivity (based on an oral glucose tolerance test (OGTT) at 12 weeks and 1 year
- An improvement in quality of life, anxiety and depression scores (as measured by PHQ9, GAD7 and EQ-5D-3LQOL)
- A reduction in antidiabetic medication use at 12 weeks and 1 year

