### 6. Study Design

Participants that are eligible and consent to take part in the study will be given an appointment to attend the Cambridge Clinical Research Centre (CCRC) at Addenbrooke's Hospital to participate in the study.

Participants will be commenced on a 12 week total diet replacement after which they will follow a stepped food reintroduction phase (weeks 13-18) and will then be followed up through a weight loss maintenance phase (weeks 19-52). Participants will be monitored throughout the year and will be seen for investigations and study procedures at the Clinical Research Facility.

- Total Diet Replacement phase - Participants will be seen face to face for metabolic investigations at baseline, week 4, week 8 and week 12. During this time the participants will be closely monitored with weekly phone calls, which will be increased if needed – this is mainly to avoid hypoglycaemia following the introduction of the LED.
- Stepped Food Reintroduction - Participants will be seen at week 16 for metabolic investigations and will be closely monitored with two-weekly phone calls which will be increased if needed to

maintain optimal glycaemic control. At the start of stepped food reintroduction orlistat 120mg three times a day will be prescribed and commenced, in line with standard practice.

- Weight loss maintenance - Participants will be seen at week 24, 36 and 52 and from week 24 will be followed up with four-weekly phone calls which will be increased if needed.

See Appendix B for a schedule of investigations and procedures.

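### Section 9 does not say which series repeated-measures ANOVA covers; if it is the study visits, anyone with one missed visit drops out of that supportive analysis

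*Protocol*

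**What the plan says.** Section 9 describes a single-arm pilot in which "participants will serve as their own controls i.e. before and after analysis". Student's t test is named for parametric data; for the rest, "comparisons will be performed using a Wilcoxon signed rank test". For more than two time points one method is given: "Changes of sequential data within experiments were evaluated by repeated measures ANOVA". No variable, visit or test is named in that sentence.

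The protocol contains three kinds of series to which it could apply:

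- **Study visits (Section 6).** "Participants will be seen face to face for metabolic investigations at baseline, week 4, week 8 and week 12"; then "Participants will be seen at week 16 for metabolic investigations"; then "Participants will be seen at week 24, 36 and 52". That makes eight visits: weeks 0, 4, 8, 12, 16, 24, 36 and 52.
- **MRI (Section 7.5).** Four times: baseline, 3 months, 6 months and 1 year.
- **Glucose tolerance test (Section 7.8).** Samples every half hour over three hours, so seven samples from 0 to 180 minutes within one test.

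The primary endpoint (Section 3.2) is "A reduction in HbA1c at 12 weeks". The secondary endpoints (Section 3.3) are mostly of the form "A reduction in triglycerides at 12 weeks and 1 year". Section 4.4 plans 20 to 30 participants.

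**The concern.** Classical repeated-measures ANOVA needs a full row of values for each participant. Over eight visits, one missed visit takes that person's seven other values out of the test. In a rare disease with 20 to 30 participants those values are costly to collect and hard to replace.

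The visit reading is plausible. One aim in Section 3.1 is to follow metabolic control for a year, and the ANOVA is the only method listed for more than two time points. The protocol thus names a method that needs complete rows for a series it leaves undefined. At stake are the over-time analyses, not the listed 12-week and 1-year comparisons.

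**Working it through.** The plan states no power, dropout or missed-visit figure, so there is none to reproduce. The inputs from the protocol are N = 20 or 30 (Section 4.4), 8 visits (Section 6) and 4 MRI times (Section 7.5). Baseline is taken as always present. All miss rates and patterns below are assumptions.

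**1. Does the method need complete rows?** A standard repeated-measures ANOVA routine runs on a full table of 20 people by 8 visits (160 values). It stops, reporting unbalanced data, once one value is removed. The person must then be dropped or the value imputed.

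**2. Independent misses at rate p per post-baseline visit.** Expected complete records are N(1−p)^7 for the visits and N(1−p)^3 for MRI. For the visits, the share of collected values left unused is 1 − 8(1−p)^7 / (1 + 7(1−p)).

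| p | Complete, 8 visits (N = 20 / 30) | Unused, 8 visits | Complete, MRI (N = 20 / 30) |
|---|---|---|---|
| 2% | 17.4 / 26.0 | – | 18.8 / 28.2 |
| 5% | 14.0 / 21.0 | 1 − 5.587/7.65 = 27% | 17.1 / 25.7 |
| 10% | 9.6 / 14.3 | 1 − 3.826/7.30 = 48% | 14.6 / 21.9 |

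For comparison, a baseline and week-12 pair at p = 10% keeps 20 × 0.9 = 18 or 30 × 0.9 = 27.

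**3. Other patterns, eight visits.**

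- *Dropout of 20% by week 52, at a random visit.* This leaves 16 of 20 or 24 of 30 complete. A person who drops out has on average 4 values, so the unused share is 4×4/(16×8 + 16) = 16/144 = 11%. At N = 30 it is 24/216, the same share.
- *The same 10% of people miss every post-baseline visit.* This leaves 18 of 20 or 27 of 30 complete. Unused: 2/(8×18 + 2) = 2/146 = 1.4%, or 3/219 = 1.4%.
- *Three people miss one visit each.* Unused: 7×3/(160 − 3) = 21/157 = 13%, or 21/237 = 9%.

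**4. Effect on the over-time test (illustrative simulation).** The assumptions were a mean path that falls to week 12 and partly returns, serially decaying correlation, and values missing completely at random. The effect was set so that Greenhouse-Geisser-corrected ANOVA on full data has 80% power. On complete cases power falls to:

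- 53–59% with independent misses of 5%
- 31–36% with independent misses of 10%
- 64–67% with 20% dropout
- 73–74% with the clustered 10% pattern

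The Monte Carlo standard error is up to 1.8 points. These figures show the ordering of the patterns; they do not predict this trial.

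**The case against.** **The sentence may not be about visits.** Its wording points to data within an experiment, and Section 9 describes comparison across time separately as before and after. The glucose tolerance curve is an obvious within-experiment series. This stands: nothing in the document makes the visit reading the more likely one, so the point is conditional. The request to name the series holds on either reading.

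**Detail may sit in a statistical analysis plan.** This stands for handling of missed visits and for a sphericity correction. A reader might infer that the test would reject too often. In simulation with eight visits and serially decaying correlation, the uncorrected test did so (7.6–11.1% at a nominal 5%), but Greenhouse-Geisser gave 3.9–4.8%. Such a correction may be planned elsewhere, so this is no finding. The choice of method is different, because the protocol itself names it. Software that fits a mixed model when values are missing is using another method than the one stated.

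**No listed endpoint depends on it.** This stands. The questionnaire endpoint has no time point in Section 3.3, but Section 3.1 places it at the end of the intervention, again a before/after comparison.

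**The replacement can go wrong too.** This stands in part. A mixed model with a random intercept, exponential correlation and one common variance held its level when that form was true (4.4–5.1%). It gave 7.1–7.9% when the baseline SD was 1.5 times the later SD, and 6.5–6.9% when response varied between people. Those runs used full data and approximate degrees of freedom. Greenhouse-Geisser ANOVA gave 4.3–5.7% in the latter two settings. The covariance therefore needs care.

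**Conclusion.** The point holds in a limited, conditional form and is minor. Section 9 leaves the series undefined. If the study visits or MRI times are meant, classical repeated-measures ANOVA discards every partly observed participant. The size of the loss is unknown, because the documents give no miss rate: about 30% to 52% of participants under independent misses of 5% to 10% over eight visits (1 − 0.698 and 1 − 0.478), but only 1.4% of collected values if misses fall on the same people. The eight-visit figures apply only to measures taken at every visit.

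A reader might infer that the primary result is at risk, or that half the sample will be lost. The documents support neither. The primary endpoint and the 12-week and 1-year secondary endpoints are covered by the paired tests, and the larger losses require scattered misses at an assumed 10% per visit.

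**What to change.** State in Section 9 which variables and time points the ANOVA sentence covers. If it is only the samples within one glucose tolerance test, say so and change nothing else. If visits are meant, replace the sentence along these lines:

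> Repeated-measures ANOVA will be used only for complete series within one test, such as the OGTT samples. Changes across more than two study visits will be analysed by a linear mixed model (REML) using all observed visits, with visit as a categorical fixed effect, a pre-specified within-participant covariance that lets both variance and correlation differ across visits, and small-sample degrees of freedom. This analysis is supportive; the paired t or Wilcoxon tests of the 12-week and 1-year endpoints are unchanged.

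A random intercept alone, or a form with one common variance, is not enough. A fully unstructured matrix over eight visits has 8×9/2 = 36 parameters, which is many for 20 to 30 participants. Separate visit variances with correlation that decays with time (8 variances plus one correlation parameter) is one workable choice. No transformation rule is needed to keep partial records.

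Cost: a few sentences and no new data. The covariance must be fixed in advance. The over-time test may be somewhat conservative, or modestly liberal if the chosen structure is wrong. If misses are few or fall on the same people, the gain is small.

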## 10. Reimbursement

Participants will have travel and overnight accommodation costs covered.

## 11. Sponsor

The study is jointly sponsored by Cambridge University Hospitals NHS Foundation Trust and the University of Cambridge.

## 12. Insurance

The design of the study will be insured through the University of Cambridge (joint sponsor). The University Insurance Office have advised that insurance for negligent and non-negligent harm under the University's Clinical Trials policy can be arranged if this trial is approved by the NHS Ethics Committee. The University's insurers are Newline, the insurance policy reference is B0823Q31000177/WD1600523 and the Limit of Indemnity under the policy is £10,000,000 each and every claim. In addition named members of the research team will have insurance cover provided through the NHS indemnity scheme.

## 13. Summary of Main Issues

### 13.1 Management of Incidental Findings

Throughout the course of the study there is a possibility that incidental findings of clinical relevance are made during clinical, biochemical and radiological and psychological studies. In this instance the

study doctor will interpret the findings, disclosing them to the participant and referring on for further clinical investigation if necessary. Participants will be asked to consent as to whether they would like their GP informed of these study findings.

### 13.2 Side Effects of Diet

- There are some common transient side effects related to coming off a normal diet with a considerable reduction in energy intake. These include headaches, some dizziness, feeling cold and constipation. A fibre supplement will be prescribed to alleviate constipation.
- Low blood sugars may occur due to the reduction in calorie consumption and antidiabetic medication may need to be adjusted. At the start of the diet medication will be reviewed by a clinical doctor and insulin will be reduced in anticipation of a fall in blood sugars and some antidiabetic medicine will be stopped. Insulin adjustments will be titrated as needed and there will be regular telephone and email contact between participants and the study team to review blood sugars and amend insulin doses as necessary.

### 14. Dissemination

The results will be published in scientific literature and presented at scientific conferences. All information that is published and presented will be anonymous. Results will be shared at the Lipodystrophy Support Group Day, co-hosted by the NSIR service and Lipodystrophy UK (a charity based in the UK that provides support and information to patients with lipodystrophy and their families) and in the annual SIR Service newsletter.

## Appendix A- Screening Visit Proforma

| VLCD and Lipodystrophy Screening Visit                            |                          |       |                          |
|---|--------------------------|-------|--------------------------|
| Patient Details  |                          |       |                          |
| Name:   | Date of birth:           |       |                          |
| Sex:  | Ethnicity:               |       |                          |
| Pregnant   |                          |       |                          |
| Yes   |  | No    |  |
| Clinical assessment at most recent clinical appointment    |                          |       |                          |
| Weight(Kg):   | Height(cm):              |       |                          |
| BMI(kg/m  ):  |                          |       |                          |
| Weight stable for last 3 months?                           |                          |       |                          |
| Yes   |  | No    |  |
| Biochemical assessment at most recent clinical appointment |                          |       |                          |
| Parameter   | Value                    | Units | Date tested              |
| HbA1c   |                          |       |                          |
| TSH   |                          |       |                          |
| T4  |                          |       |                          |
| Previous gastric bypass/ banding                           |                          |       |                          |
| Yes   |  | No    |  |
| History of an eating disorder/ purging behaviour           |                          |       |                          |
| Yes   |  | No    |  |
| Diabetic Eye Screening                                     |                          |       |                          |
| Date of most recent screening:                                    |                          |       |                          |
| Results of most recent screening:                                 |                          |       |                          |

**Retinopathy diagnosis**

Yes  No

If yes:

Background retinopathy  Pre-proliferative retinopathy  Proliferative retinopathy

**Treatment for retinopathy:**

**Medication Review (check for steroids, immunosuppressant's, antipsychotics, leptin therapy)**

**Food Diary Given**

Yes  No

Comments related to Food Diary

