## 1. Background and Rationale

Lipodystrophy is a rare condition characterised by a paucity of body fat due to the absence or dysfunction of adipocytes (fat cells). It can be inherited or acquired in origin and can result in a total (generalised lipodystrophy) or partial loss of adipose tissue (partial lipodystrophy). It has been estimated that there are 1.3–4.7 cases of lipodystrophy per million people worldwide (Dhankhar 2017). Due to the lack of fat storage capacity, excess lipid accumulates in other tissues such as the liver, pancreas and muscle where it impairs insulin action and contributes to the pathogenesis of several metabolic disorders including diabetes, non-alcoholic fatty liver disease and pancreatitis.

As fat transplantation or correction of the underlying genetic defect have yet to become viable therapeutic options, current therapeutic approaches focus on preventing and managing the metabolic complications of lipodystrophy using standard approaches used to treat obese patients with similar metabolic problems including agents such as metformin, gliptins, statins, fibrates and/or insulin (Brown et al. 2016). Advice for the dietary management of lipodystrophy is based on the evidence available from studies in patients with type 2 diabetes, cardiovascular disease and high triglycerides (Stears & Hames 2014). The general advice for all patients with lipodystrophy includes calorie and fat restriction (Brown et al. 2016). However, this approach is currently based on clinical experience rather than experimental evidence. Four case reports on patients with congenital generalised lipodystrophy describe improvements in blood glucose and triglycerides after restricting calorie and fat intake (Joannie et al. 2017; Kazlauskaitė et al. 2001; Santos & Chvng 2017; Keenan et al. 1980), however there are currently no published studies.

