## 4. Recruitment

Patients with partial lipodystrophy referred to our centre and who meet the inclusion criteria will be invited to take part in the study. A computerised search of medical records of patients attending the National Severe Insulin Resistance (NSIR) Service will be conducted by the clinical care team and potentially eligible participants will be invited to participate in the study. Potential participants will be invited at clinical appointments, via telephone calls, letters or email. They will be provided with an invitation letter and a patient information sheet along with contact details of the study team. Potential participants will be contacted to answer queries and ascertain interest.

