### 4.1 Inclusion criteria

- Familial Partial Lipodystrophy
- Age  $\geq$  18 yrs
- T2DM
- Willingness to check daily blood sugars
- HbA1c between 53mmol(7%)- 108 mmol(12%)
- Weight stable for 3 months
- Capacity to consent

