### 4.2 Exclusion criteria

- Pregnancy
- Untreated thyroid dysfunction (patients who have been euthyroid on medication for at least 3 months can be included)
- Use of medication that adversely affects diabetes control (e.g. steroids/ immunosuppressants/ certain antipsychotics)
- Incapacity to give informed consent

- History of an eating disorder/ purging behaviour
- Previous gastric bypass/ banding
- Use of leptin therapy
- Untreated proliferative retinopathy

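### Does the screening form need to ask when antidiabetic or lipid-lowering treatment was last changed?

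*Protocol*

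**What the plan says.** Protocol 4.1 requires "Weight stable for 3 months". Protocol 4.2 excludes untreated thyroid dysfunction but adds that "patients who have been euthyroid on medication for at least 3 months can be included". Neither section sets a stability period for antidiabetic or lipid-lowering drugs.

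The Appendix A screening form carries the line "Medication Review (check for steroids, immunosuppressant's, antipsychotics, leptin therapy". All the drugs it names come from the exclusion list in Protocol 4.2.

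Protocol 1 describes the usual treatment of this disease as including "agents such as metformin, gliptins, statins, fibrates and/or insulin". The primary endpoint (Protocol 3.2) is "A reduction in HbA1c at 12 weeks". One secondary endpoint (Protocol 3.3) is "A reduction in triglycerides at 12 weeks and 1 year", and another is lower antidiabetic medication use at the same times. Protocol 9 states that "participants will serve as their own controls i.e. before and after analysis".

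Other places where treatment history could be recorded are:
- the recruitment search (Protocol 4), which is "A computerised search of medical records of patients attending the National Severe Insulin Resistance (NSIR) Service";
- the baseline clinical history, kept in a case record file (Protocol 7.1);
- the medication review ticked at baseline and at each week of the diet phase (Appendix B);
- the doctor's review of medication at the start of the diet (Protocol 13.2).

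**The concern.** The protocol asks for three months of stability in weight and in treated thyroid disease, but not in the drugs that act most directly on HbA1c and triglycerides. The form that screens medication looks only for reasons to exclude.

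In a before-and-after study this could matter. Suppose antidiabetic treatment was intensified at a clinic visit shortly before entry, and HbA1c was still falling at baseline. The rest of that fall would be credited to the diet, with no control group to show it. A recent fibrate or statin change could do the same to triglycerides. If the date of the change is never collected, a later analysis cannot set those participants aside. A false or inflated 12-week reduction is what would be at stake.

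**Working it through.** **What the text leaves open.** The protocol gives no SD, effect size or power calculation behind its 20-30 participants, so there is no planned figure to reproduce. The first question is whether the missing prompt means missing information.

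- Appendix A's clinical items follow the entry criteria: pregnancy, weight stability, HbA1c, thyroid tests, gastric surgery, eating disorder, retinopathy and excluded drugs. A prompt for excluded drugs is what such a checklist needs.
- The baseline regimen has to be recorded somewhere, because reduced antidiabetic medication use is a secondary endpoint and cannot be assessed without it.
- The scheduled baseline medication review, the medical history and the clinic's own records can all hold dates. None of these passages requires the date of the last change, so capture is likely but not guaranteed. The case record file is not part of the protocol.

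**How large could the effect be?** All inputs below are assumptions.

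Let a share f of participants have a residual HbA1c fall d at baseline. The mean bias is f × d. With f = 0.25 and d = 8 to 10 mmol/mol, it is 0.25 × 8 = 2.0 to 0.25 × 10 = 2.5 mmol/mol.

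Simulation (200,000 trials per setting): each change is Normal(0, SD), minus d in a random 25% of participants. The test is a two-sided one-sample t test at 0.05. The figure is the chance of a significant fall when the diet does nothing; the nominal value is 2.5%.

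| Setting (25% changed, d = 8-10) | n=20 | n=30 |
|---|---|---|
| All changes still lowering HbA1c, SD 10-12 | 10-16% | 13-23% |
| The same, SD 20 | 6.1-7.4% | 7.5-9.5% |
| Half lowering, half raising, SD 10-20 | about 2.5% | about 2.5% |
| All lowering, offset by an equal upward push in everyone, SD 10-12 | about 2.4% | about 2.4% |
| The same, upward push twice the mean drift, SD 10-12 | 0.2-0.4% | 0.1-0.2% |

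The last two rows represent the insulin reductions and stopped drugs at diet start (Protocol 13.2), which push HbA1c up. Depending on the inputs, the error ranges from well above nominal to well below it.

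**Against a detectable effect.** For f = 10-30% and d = 5-10, the bias runs from 0.10 × 5 = 0.5 to 0.30 × 10 = 3.0 mmol/mol. With an SD of change of 10-20, the change detectable with 80% power by a paired t test is 6.7-13.3 mmol/mol at n=20 and 5.3-10.6 at n=30. The bias is therefore smaller than any effect the study could reliably detect.

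**What a restricted analysis would give.** The 95% half-width is t(0.975, m−1) × SD/√m for m participants. With SD 10-12:

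- n=20: 2.093 × 10/√20 = 4.7, and 5.6 at SD 12. With 25% set aside (m=15): 5.5-6.7. With 40% set aside (m=12): 6.4-7.6.
- n=30: 3.7-4.5. With 25% set aside (m=22 or 23): 4.3-5.3. With 40% set aside (m=18): 5.0-6.0.

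The restricted estimate would be less precise. It would also leave in place the drug reductions at diet start, which are the one medication confounder that the protocol documents.

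**The case for a change.** The strongest case for a change is that it is cheap and can only be made in advance. An analysis plan can add a sensitivity analysis, but it cannot analyse a date that was not collected for everyone. The protocol already accepts the principle for weight and thyroid status, and the same form has date fields for HbA1c and eye screening. Participants come from a treating clinic and may be invited at appointments, where treatment may well be adjusted. One more field would exclude nobody. If the diet effect is large, the restricted analysis would simply confirm it.

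Much of this stands. The visible text does not ensure that the date is captured, and recording it prospectively is better than searching for it later. What does not stand is that recent changes could not be checked without the field, since several sources may supply the dates. Nor is the form where the gap arises: that is the absence of a stability condition in Protocol 4.1 and 4.2. Adding such a condition could cost recruits in a rare disease with a target of 20-30, so its absence is a fair trade-off.

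**Conclusion.** No change is needed. The observation is accurate as far as it goes: the protocol sets no stability period for antidiabetic or lipid-lowering treatment, and does not explicitly ask for the date of the last change. This is a gap in detail of the kind normally filled by the case record form and the analysis plan. It does not contradict anything in the protocol, and filling it would alter no stated rule, number or main result.

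The possible harm rests wholly on assumed frequency, size and direction. With every recent change assumed to lower HbA1c, the false-positive chance could reach 10-16% at n=20 or 13-23% at n=30 (25% changed, 8-10 mmol/mol still to fall, SD 10-12). With mixed directions, or an equal offset from the drug reductions at diet start, it stays near the nominal 2.5%. No size can be given for triglycerides. Investigators who wish to could note drug, dose and date of last change at the baseline medication review, and report the 12-week changes with and without recently changed participants. That is an optional refinement for a pilot study, and it would not deal with the medication changes made at diet start.
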